5.2.6 Other subject characteristics

Not applicable.

5.3 Study treatment duration and compliance

5.3.1 Study treatment duration

Double-blind treatment duration is defined as the number of days between the first dose of double-blind study treatment [see definition in Section 11.2] and the last dose of double-blind study treatment [see definition in Section 11.4] plus one day, without taking into account interruptions. For the purpose of tabulation treatment duration will also be expressed in weeks, calculated by dividing the above treatment duration (in days) by 7.

In addition, run-in treatment duration is defined as the number of days between the first dose and last dose of open-label placebo run-in treatment.

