3.2 Study design rationale

This study is designed to select doses to be investigated in the Phase 3 program. The design of this dose-finding study meets the requirements laid out by international guidelines [ICH 2000a, ICH 2000b, EMA 2010] and literature [Rose 1990, Myers 2001].

In accordance with the regulatory guidelines, the study has a placebo run-in period of 4 to 6 weeks. The administration of placebo during this period minimizes bias due to the regression-toward-the-mean phenomenon [EMA 2010]. The placebo run-in period is 4 weeks for anti-hypertensive treatment-naïve subjects at Visit 1. For subjects receiving anti-hypertensive treatment at Visit 1, a 2-week placebo wash-out period is added to the 4-week run-in period. For these subjects the SB placebo run-in period is 6 weeks.

A 2-week SB placebo withdrawal period is introduced at the end of the study to investigate the withdrawal phenomena, i.e., rebound effect on BP.

^{**} Only for women of childbearing potential.

DB = double-blind; EOS = End-of-Study; EOT = End-of-Treatment; FU = follow-up, SB = single-blind, WD = withdrawal.

Essential hypertension Protocol AC-080A201 Version 3 30 May 2016, page 38/112

Confidential

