5.1.4.1 Run-in period (single-blind placebo)

Subjects will receive 2 bottles; one bottle contains placebo capsules matching ACT-132577 and the other bottle contains placebo capsules matching lisinopril. The subjects must be instructed to take one capsule from each bottle (i.e., total of 2 capsules) o.d. every morning from the morning of the Screening visit (Visit 1) to the morning of Visit 4 / Pre-randomization (Day -1). The run-in period is an SB period (subject-blinded). Accordingly, site staff must not inform the subject of the treatment received during this period.

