8.1.4.1 Day -1 (Visit 4 / Pre-randomization)

The Day -1 visit must be scheduled 7 days \pm 2 days after Visit 3.

Visit 4 / Pre-randomization includes:

- Sitting BP and HR, and standing BP, measured by OBPM device at trough.
- Physical examination and body weight.
- *12-lead ECG.
- *Laboratory tests (i.e., hematology, blood chemistry, and pregnancy test if applicable).
- *Urinalysis (dipstick by site / UACR by central laboratory).
- Reporting of AEs and SAEs.
- Recording of changes in concomitant medications.
- *Assessment of childbearing potential and recording of changes in contraception methods, if applicable.
- *Record the date and time of last study treatment intake before this visit
- Check compliance with study treatment.

The investigator checks the following eligibility criteria and decides on the eligibility of the subject for randomization:

- Mean SiDBP \geq 90 to < 110 mmHg measured by OBPM device.
- Treatment compliance ≥ 80% during run-in period.
- 1) If one of these criteria is not met, the subject must be discontinued from the study. In such case, tests highlighted by * are optional and performed as deemed necessary per medical practice. The investigator has to record the reason of the run-in failure in the eCRF. A follow-up telephone call must be performed in 2 weeks to check any potential AEs/SAEs.

Essential hypertension Protocol AC-080A201 Version 3 30 May 2016, page 70/112

Confidential

2) If all these criteria are met, perform the following:

- Apply the ABPM device according to the BP manual for 24 h recording and review the subject's instruction handout with the study participant.
- Administer the last doses of the run-in period study treatment. Record the study treatment intake date and time and retrieval of study treatment bottles.
- Instruct subject to return to the site the next morning.

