5.3.2 Compliance with study treatment

Double-blind treatment compliance is based on the **Study Drug Dispensing & Accountability** eCRF. Run-in treatment compliance is based on the same eCRF.

As per section 5.1.4.2 of the protocol, all subjects had to take 2 capsules o.d. every morning from the morning of Visit 4 / Randomization (i.e., Day 1, after completion of the baseline 24-hour ABPM recording) to the morning of Visit 7 / Part 1.

Compliance between Visit 4 and Visit 7 / Part 1 will be then calculated as follows:

Compliance =
[(number of capsules dispensed at Visit 4 – number of capsules returned at Visit 6 +
number of capsules dispensed at Visit 6 – number of capsules returned at Visit 7)/
(Total number of capsules that should have been taken)] × 100.

The number of capsules that should have been taken during the double-blind period is the double-blind treatment duration (in days) as defined in Section 5.3.1, multiplied by 2.

Run-in compliance between Visit 1 and Visit 4 / Part 1 will be calculated similarly.

Here the expected number of capsules is the run-in treatment duration (in days) as defined in Section 5.3.1, multiplied by 2.

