11.9 Study day

The study day is the number of days elapsed since the day of first DB treatment plus 1 (start of DB treatment is considered Day 1). For dates prior to Day 1, study day is the negative number of days between the date under consideration and the date of first DB treatment. Therefore, the study day is always different from zero.

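### Run-in duration in SAP 5.3.1 is counted one day short, which leaves the expected capsule count for run-in compliance two capsules short

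*SAP*

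**What the plan says.** - **Run-in duration (SAP 5.3.1):** "run-in treatment duration is defined as the number of days between the first dose and last dose of open-label placebo run-in treatment".
- **Double-blind duration (same section):** also the days from first to last dose, but "plus one day, without taking into account interruptions".
- **Expected run-in capsules (SAP 5.3.2):** "Here the expected number of capsules is the run-in treatment duration (in days) as defined in Section 5.3.1, multiplied by 2". The section presents the run-in calculation as parallel to the double-blind one.
- **Dosing days (Protocol 5.1.4.1):** two capsules "o.d. every morning from the morning of the Screening visit (Visit 1) to the morning of Visit 4 / Pre-randomization (Day -1"). On Day -1, for subjects who meet the randomization criteria, Protocol 8.1.4.1 says: "Administer the last doses of the run-in period study treatment".
- **Length (Protocol 3.2):** "The placebo run-in period is 4 weeks for anti-hypertensive treatment-naïve subjects at Visit 1". For previously treated subjects: "For these subjects the SB placebo run-in period is 6 weeks".
- **Use:** run-in duration and run-in compliance are summarized on the Run-in Set (SAP 10.5.1, 10.5.2, 13.4.1 and 13.4.2). Compliance is cut at below 80%, 80–120% and above 120%. SAP 7.1.2 puts anyone with at least one run-in dose in that set.

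**The concern.** The two periods have the same dosing pattern, one intake per morning with the first and last mornings both dosed, but their durations are counted by different rules and no reason is given. The run-in rule leaves out one of the two end days. That shortens the reported run-in duration and shrinks the compliance denominator, so a fully adherent subject can score above 100%. The lower cut of the compliance table is also the threshold for randomization (at least 80%, Protocol 4.3 and 5.1.9.2), so a shift at that cut can make the table look inconsistent with the eligibility decisions made at the sites.

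**Working it through.** The plan states no run-in compliance figure to reproduce, so the check is direct arithmetic on the definitions.

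**Meaning of the day count.** SAP 11.9 uses the same phrase for dates before Day 1: "study day is the negative number of days between the date under consideration and the date of first DB treatment". That is a plain date difference. The double-blind definition points the same way, since its extra day would overcount if the phrase were already inclusive. SAP 11.2 and 11.3 define run-in start and end as the first and last day of intake. So:

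- D = last minus first run-in dose date (the SAP run-in duration)
- dosing days = D + 1
- SAP expected capsules = 2D; inclusive expected capsules = 2(D + 1); shortfall = 2 capsules

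**Values of D.** Day -28 to Day -1 gives D = 27, and Day -42 to Day -1 gives D = 41. If 4 or 6 weeks is taken as the difference itself, D = 28 or 42.

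**Effect on compliance when the count follows the last dose.** For C capsules taken, SAP compliance is C/(2D) and inclusive compliance is C/(2(D + 1)). The ratio is (D + 1)/D, a relative overstatement of 1/D. A true value shows as 80% when it equals 80 × D/(D + 1), and as 120% when it equals 120 × D/(D + 1).

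| D | Full adherence shows as | True value shown as 80% | True value shown as 120% |
|---|---|---|---|
| 27 | 28/27 = 103.7% | 77.1% | 115.7% |
| 28 | 29/28 = 103.6% | 77.2% | 115.9% |
| 41 | 42/41 = 102.4% | 78.1% | 117.1% |
| 42 | 43/42 = 102.4% | 78.1% | 117.2% |
| 14 | 15/14 = 107.1% | 74.7% | 112.0% |
| 7 | 8/7 = 114.3% | 70.0% | 105.0% |
| 0 | undefined (division by zero) | – | – |

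At a true 80% the shift in a full-length run-in is 1.9 to 3.0 percentage points. In whole capsules, one or two counts per duration cross the lower cut. At D = 27 it is 44 capsules (44/54 = 81.5% against 44/56 = 78.6%). At D = 41 it is 66 and 67 (80.5% and 81.7% against 78.6% and 79.8%).

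**If the count precedes the Day -1 dose.** A fully adherent randomized subject is then recorded with 2D capsules taken. The SAP denominator gives 2D/2D = 100%, and an inclusive denominator gives 27/28 = 96.4% or 41/42 = 97.6%. The duration itself is one day short on either reading.

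**The case against.** The strongest objection concerns when capsules are counted. Protocol 8.1.4.1 lists the compliance check and the eligibility decision before the last run-in dose, and bottle retrieval after it. Protocol 5.1.9.1 requires the inventory before further treatment is provided. If the recorded return count precedes the Day -1 dose, the SAP formula is exactly right for a fully adherent randomized subject, and adding a day alone would understate compliance. This stands as a condition on the direction of the compliance error. It does not justify the different rules: Visit 7 / Part 1 has the same order of steps (Protocol 8.2.4.1), and there the SAP adds the day. Nor does it touch the duration output.

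A reader might also infer three stronger things that the documents do not support:

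- **That every run-in compliance value is too high by a fixed 2.4–3.6%.** The error is 1/D. It is 3.7% on the nominal 4-week schedule, larger for early discontinuers, and conditional on count timing.
- **That the rule hides breaches of the randomization criterion.** Eligibility is calculated by the site with the protocol formula (Protocol 5.1.9.2), not with the SAP value, and deviations at Visit 4 / Pre-randomization have their own category (SAP 6). The criterion also has no upper bound, so only the 80% cut is shared with the table.
- **That the SAP value disagrees systematically with the site's.** The site denominator is the number of capsules due in the period. The documents do not say how sites count days or whether they include the Day -1 dose.

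**Conclusion.** The run-in definition is wrong as written and inconsistent with the double-blind one. Run-in duration is one day short and expected capsules are two short, given dosing on both end days as Protocol 5.1.4.1 requires.

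The size of the compliance error rests on the returned count being taken after the Day -1 dose. On that assumption the relative overstatement is about 3.6–3.7% for a 4-week run-in and 2.4% for a 6-week run-in, rising to 7.1% at D = 14 and 14.3% at D = 7, with no defined value for a single dosing day. In a full-length run-in, misclassification is confined to the narrow bands just below 80% and above about 116–117%.

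The consequence is minor. It is limited to the descriptive run-in duration and compliance outputs. PPS exclusion uses double-blind compliance (SAP 6), which already has the extra day, and no efficacy analysis uses the run-in value.

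**What to change.** In SAP 5.3.1, define run-in duration as last minus first run-in dose date plus one day. In SAP 5.3.2, state that the returned-capsule count used is taken after the Day -1 dose, so that numerator and denominator cover the same days. The two changes belong together, because the first without the second could replace an overstatement with an understatement.

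As an editorial point, replace open-label with single-blind in the run-in definition, to match Protocol 5.1.4.1 and SAP 2.1 and 7.1.2. This changes no calculation.

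The cost is a few words in the SAP, one derivation line, and a rerun of the run-in duration and compliance outputs. No new data are needed, provided the recorded return counts reflect the bottles as retrieved after the Day -1 dose; that should be confirmed against the accountability log.

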5.3.2 Compliance with study treatment

Double-blind treatment compliance is based on the **Study Drug Dispensing & Accountability** eCRF. Run-in treatment compliance is based on the same eCRF.

As per section 5.1.4.2 of the protocol, all subjects had to take 2 capsules o.d. every morning from the morning of Visit 4 / Randomization (i.e., Day 1, after completion of the baseline 24-hour ABPM recording) to the morning of Visit 7 / Part 1.

Compliance between Visit 4 and Visit 7 / Part 1 will be then calculated as follows:

Compliance =
[(number of capsules dispensed at Visit 4 – number of capsules returned at Visit 6 +
number of capsules dispensed at Visit 6 – number of capsules returned at Visit 7)/
(Total number of capsules that should have been taken)] × 100.

The number of capsules that should have been taken during the double-blind period is the double-blind treatment duration (in days) as defined in Section 5.3.1, multiplied by 2.

Run-in compliance between Visit 1 and Visit 4 / Part 1 will be calculated similarly.

Here the expected number of capsules is the run-in treatment duration (in days) as defined in Section 5.3.1, multiplied by 2.

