5.1.4 Study treatment administration

Study treatment is supplied in bottles containing 36 capsules to provide 36 days of treatment to cover a 4-week treatment period and the time window to the next visit.

Study treatment consists of 2 bottles. The subjects must be instructed to take one capsule from each bottle (i.e., total of 2 capsules) orally o.d. irrespective of food intake every morning between 7:00 and 10:00 a.m., and not to take it on the morning of study visit days.

See Table 1 and Section 8 for details on study treatment dispensing.

^{*} Nine visits: Only for women of childbearing potential.

Essential hypertension Protocol AC-080A201 Version 3 30 May 2016, page 44/112

Confidential

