8.2 Double-blind period

8.2.1 Day 1 (Visit 4 / Randomization)

Day 1 is the start of DB treatment period for subjects eligible after Day -1 assessments (Visit 4 / Pre-randomization).

Day 1 includes:

- Remove the 24-h ABPM device.
- Reporting of AEs and SAEs.
- Recording of changes in concomitant medications.
- Access IRT and obtain randomization and bottle numbers. Dispense the DB period study treatment.
- Instruct subject to take one capsule from each bottle irrespective of food intake every morning between 7:00 and 10:00 a.m.
- Study treatment intake at site.
- Remind the subject to bring back both bottles to the next visit and not take study treatment on the day of study visit prior to coming to the site.

8.2.2 Visit 5 / Week 2

This visit will be performed at Day 14 ± 3 days. The subject must not take study treatment at home on the morning of Visit 5.

Visit 5 includes:

- Sitting BP and HR, and standing BP, measured by OBPM device at trough.
- Physical examination and body weight.
- Laboratory test (i.e., hematology, blood chemistry, and pregnancy test if applicable).
- •
- Urinalysis (dipstick by site / UACR by central laboratory).
- Reporting of AEs and SAEs.
- Recording of changes in concomitant medications.

Essential hypertension Protocol AC-080A201 Version 3 30 May 2016, page 71/112

Confidential

- Assessment of childbearing potential and recording of changes in contraception methods, if applicable.
- Record the date and time of last study treatment intake before this visit.
- Check compliance with study treatment.
- Study treatment intake at site. Record the study treatment intake date and time.
- Instruct subject to continue taking one capsule from each bottle irrespective of food intake every morning between 7:00 and 10:00 a.m.
- Remind the subject to bring back both bottles to the next visit and not take study treatment on the day of study visit prior to coming to the site.

8.2.3 Visit 6 / Week 4

This visit will be performed at Day 28 ± 3 days. The subject must not take study treatment at home on the morning of Visit 6.

Visit 6 includes:

- Sitting BP and HR, and standing BP, measured by OBPM device at trough.
- Physical examination and body weight.
- 12-lead ECG.
- Laboratory test (i.e., hematology, blood chemistry, and pregnancy test if applicable).
- Urinalysis (dipstick by site / UACR by central laboratory).
- Reporting of AEs and SAEs.
- Recording of changes in concomitant medications.

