- Assessment of childbearing potential and recording of changes in contraception methods, if applicable.
- Record the date and time of last study treatment intake before this visit.
- Check compliance with study treatment and retrieve study treatment bottles.
- Access IRT to obtain new bottle numbers and dispense 2 new study bottles.
- Study treatment intake at site. Record the study treatment intake date and time.
- Instruct subject to take one capsule from each bottle irrespective of food intake every morning between 7:00 and 10:00 a.m.
- Remind the subject to bring back both bottles to the next visit and not take study treatment on the day of study visit prior to coming to the site.

Essential hypertension Protocol AC-080A201 Version 3 30 May 2016, page 72/112

Confidential

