8.4 Premature End-of-Treatment visit (Visit 9)

All subjects who prematurely discontinue study treatment must have Visit 9 performed as soon as possible but not longer than 7 days after the last dose of study treatment, provided that the subject's consent for this limited participation in the study has not been withdrawn.

Essential hypertension Protocol AC-080A201 Version 3 30 May 2016, page 74/112

Confidential

The following assessments are to be performed at premature EOT / Visit 9:

- Sitting BP and HR, and standing BP, measured by OBPM device.
- Physical examination and body weight.
- *12-lead ECG.
- *Laboratory test (i.e., hematology, blood chemistry, and pregnancy test if applicable).
- *Urinalysis (dipstick by site / UACR by central laboratory).
- Reporting of AEs and SAEs.
- Recording of changes in concomitant medications.
- *Assessment of childbearing potential and recording of changes in contraception methods.
- Check compliance with study treatment.
- Retrieve study treatment bottles.
- Make an appointment for the follow-up telephone call or, *for women of childbearing potential, an appointment for the follow-up visit.
- * If subject discontinued study treatment during run-in period,
- This test may not be performed, and
- For women of childbearing potential, a follow-up telephone call can be made instead of the follow-up visit.

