6 DEFINITION OF PROTOCOL DEVIATIONS

PDs include deviations from inclusion and/or exclusion criteria and deviations from the protocol during the conduct of the study, classified as per latest version of PD code list. Each PD is reported in the SDTM DV domain and categorized according to time period:

1. PD at Screening
2. PD during Run-in period
3. PD at Visit 4 / Pre-randomization

4. PD during DB treatment period
5. PD during withdrawal period and follow-up

Each PD is classified as important or not. Only important PDs during time periods 3, 4 and 5 will be summarized by treatment group for the RND set. (All PDs will be listed.)

Note that an important PD does not necessarily lead to exclusion from the PPS [see Section 7.1.6], whereas an unimportant PD may lead to exclusion from the PPS. The subset of PDs *leading to exclusion* from the PPS are:

1. Double-blind treatment duration less than 49 days: PV_PP.535.
2. No or no valid Week 8 SiDBP (hence, no primary endpoint): PV_PP.501 and PV_MM.501.
3. Anti-hypertensive treatment still ongoing at randomization: PV_MM.307.
4. Taking medication during the double-blind treatment interfering with the primary efficacy parameter (SiDBP): PV_MM.503, PV_MM.504, PV_MM.506, PV_MM.507, PV_MM.508, PV_MM.509, PV_MM.534.
5. Compliance with double-blind treatment < 80% or > 120% or treatment not taken as per protocol: PV_PP.502 and PV_MM.515.

Note that exclusion will be done on a subject basis (rather than on subject / visit basis). In this particular study this approach is not unreasonable since PDs 1–5 are related to the 8 week DB treatment period and the primary efficacy endpoint is measured at the end of that period.

The one PD *leading to exclusion* from the Pharmacokinetic (PK) Set [see Section 7.1.6] is that the PK sample for that subject/visit was not taken at trough: PV_MM.512.

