13.2 Protocol deviations

Output name	Display *	Title (Description)	Analysis set(s)**	Key	Mock layout
PRDEVA	T	Important protocol deviations during the double-blind period	FAS		LAYPD001
PRDEVI	T	Protocol deviations leading to exclusion from PPS	FAS	Yes	LAYPD002
PRDEVA	T	Important protocol deviations during run-in period	RIS		LAYPD001
PRDEV	L	Listing of protocol deviations	SCR		LSTCSR021

* T = Summary Table; L = Listing.

FAS = Full Analysis Set; PPS = Per-Protocol Set; RIS = Run-in Set; SCR = Screened Set.

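### SAP 5.3.2 omits capsules returned at Visit 9, so double-blind compliance is inflated or undefined for subjects who stop treatment early

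*SAP*

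**What the plan says.** SAP 5.3.2 adds two differences to form the numerator. The first is capsules dispensed at Visit 4 less those returned at Visit 6. The second is "number of capsules dispensed at Visit 6 – number of capsules returned at Visit 7". The denominator is the double-blind treatment duration of SAP 5.3.1 (first to last double-blind dose) multiplied by 2. No rule is given for a subject who never attends Visit 6 or Visit 7.

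Protocol 5.1.11 sends a subject who stops early to Visit 9 within 7 days of the last dose, and protocol 8.4 lists this task for that visit: "Retrieve study treatment bottles". Protocol 5.1.9.2 defines compliance as capsules dispensed minus capsules returned, over capsules due in the period, and does not tie the returns to named visits. SAP 4.1, which lists changes from the protocol analyses, covers analysis sets, secondary efficacy and safety. It does not mention compliance.

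Compliance is tabulated on the FAS and PPS as below 80%, 80–120% and above 120% (SAP 10.5.2, 13.4.2), and listed for the Safety Set (13.4.2). SAP 6 includes among the deviations that remove a subject from the PPS: "Compliance with double-blind treatment < 80% or > 120% or treatment not taken as per protocol", coded PV_PP.502 and PV_MM.515. SAP 13.2 marks the FAS table titled "Protocol deviations leading to exclusion from PPS" as a key output.

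**The concern.** For an early stopper the two halves of the ratio cover different things. The denominator ends at the last dose, while the numerator still holds every capsule left unused in the last bottles, because those are handed back at a visit the formula does not name. A subject who took every dose and then stopped would look like an over-user. A subject who took half the doses and stopped would look the same, so genuine under-use is hidden.

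The FAS table is where this shows, since the FAS keeps subjects who stop early. If stopping differs between doses, the comparison of compliance across arms would partly reflect who stopped rather than how capsules were taken. If PV_PP.502 is derived the same way, the table of PPS exclusions would also record non-compliance for subjects whose only departure was stopping.

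**Working it through.** **Inputs**

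- Capsules per bottle: 36 (Protocol 5.1.4: "Study treatment is supplied in bottles containing 36 capsules to provide 36 days of treatment").
- Bottles per dispensing: 2 (Protocol 5.1.4: "Study treatment consists of 2 bottles"), so 2 × 36 = 72 capsules at Visit 4.
- At Visit 6 the old bottles are collected and 72 more capsules issued (Protocol 8.2.3: "Access IRT to obtain new bottle numbers and dispense 2 new study bottles").
- Visit 6 timing (Protocol 8.2.3): "This visit will be performed at Day 28 ± 3 days".
- Dose: 2 capsules a day.

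Assumptions: full adherence; the dose on the day of Visit 6 comes from the new bottles; an absent Visit 6 or Visit 7 return is set to zero. The SAP does not state the last of these.

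**Check on a completer.** The documents give no compliance figure to reproduce, so the formula was tried first on a subject with Visit 6 on Day 28 and last dose on Day 55. Returned at Visit 6: 72 − 2 × 27 = 18. Returned at Visit 7: 72 − 2 × 28 = 16. Compliance = (72 − 18 + 72 − 16) / (2 × 55) = 110/110 = 100%. The formula is right for completers.

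**Early stoppers, last dose on Day d**

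- Stop before Visit 6: 72 / (2d).
- Stop after a Day 28 Visit 6: (72 − 18 + 72) / (2d) = 126 / (2d).

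| Last dose | SAP 5.3.2 | All returns counted |
|---|---|---|
| Day 1 | 72/2 = 3600% | 100% |
| Day 7 | 72/14 = 514% | 100% |
| Day 14 | 72/28 = 257% | 100% |
| Day 21 | 72/42 = 171% | 100% |
| Day 27 | 72/54 = 133% | 100% |
| Day 35 | 126/70 = 180% | 100% |
| Day 42 | 126/84 = 150% | 100% |
| Day 48 | 126/96 = 131% | 100% |
| Day 53 | 126/106 = 119% | 100% |
| Day 54 | 126/108 = 117% | 100% |

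**Sensitivity to Visit 6 timing.** With Visit 6 on Day 25 the later numerator is 48 + 72 = 120, and with Visit 6 on Day 31 it is 60 + 72 = 132. A stop on Day 48 then scores 120/96 = 125% or 132/96 = 137.5%.

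**Hidden under-use.** A subject who takes half the capsules and stops on Day 14 has used 14 of the 28 due, or 50%. SAP 5.3.2 still gives 72/28 = 257%, because before Visit 6 the numerator does not depend on what was taken.

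**If an absent return is treated as missing,** the sum cannot be formed and compliance is missing for these subjects.

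**The case against.** The strongest reply is that the percentages depend on zeros the SAP never prescribes. Read just as literally, an absent return makes compliance missing and nobody lands above 120%. That stands, so the figures are conditional. It does not rescue the rule, because the FAS table would then lose the subjects whose adherence is most in question.

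The time windows of SAP 11.1 might be thought to bring Visit 9 returns in. Table 5 has no Visit 9 row, and nothing says it applies to capsule accountability. If it did, a Visit 9 up to Day 21 would map to Visit 5, which the formula does not use. With Visit 6 on Day 28 and Visit 9 on Day 36, both fall in the Visit 6 window and only the value closest to target is kept.

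The link to PV_PP.502 is also open to challenge. SAP 6 does not cite 5.3.2, and the code list it relies on is not in the documents. Protocol 5.1.9.2 has sites calculate compliance with a formula that subtracts all returns, and treats values outside 80–120% as deviations. So the effect on recorded exclusion reasons is possible, not shown.

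Four stronger inferences are not supported:

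- *The primary analysis is affected.* SAP 6 separately excludes treatment shorter than 49 days (PV_PP.535) and absence of a valid Week 8 SiDBP (PV_PP.501). Those codes also keep early stopping visible in the exclusion table.
- *Subjects stopping on Days 49–52 leave the PPS through this formula alone.* For office readings the Week 8 window closes 5 minutes after the last dose (SAP 11.1), so a Visit 9 reading normally falls outside it. Such a subject would need an earlier in-window reading, for example at an unscheduled visit from Day 43. A last dose from Day 50 may also belong to an ordinary completer, since Visit 7 Part 1 is Day 55 ± 5.
- *About one in five FAS subjects are misclassified.* The allowance of about 20% in protocol 11.5.1 converts a PPS of 70 per group into 90 randomized. PPS losses include protocol deviations and missing Week 8 values as well as early stopping.
- *131–514% is the full range.* It covers stops from Day 7 to Day 48. Earlier stops score higher, and with Visit 6 on Day 28, stops on Days 53–54 fall below 120%.

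**Conclusion.** The point holds as an error in a stated derivation rule, and it should be corrected. SAP 5.3.2 works for completers but returns either an inflated value or no value for subjects who stop early, and it departs from protocol 5.1.9.2 without being listed as a change. With absent returns set to zero, full adherence and Visit 6 on Day 28, the distortion is large for most stop days and shrinks to about 117–119% by Days 53–54.

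What is certainly affected is descriptive: the FAS compliance table, which is not marked as a key output, and the Safety Set compliance listing. The reasons for PPS exclusion are affected only if PV_PP.502 is derived from 5.3.2. That is plausible, since 5.3.2 is the only definition of double-blind compliance in the SAP, but Section 6 does not say so. The primary dose-response analysis is essentially unaffected. How many subjects are involved cannot be worked out from the documents.

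**What to change.** In SAP 5.3.2, define the numerator as all double-blind capsules dispensed (Visits 4 and 6) minus all double-blind capsules returned at any visit, including Visit 9 and late or unscheduled returns. This restores agreement with protocol 5.1.9.2 and covers forgotten bottles, which protocol 5.1.9.1 asks subjects to bring to the next visit. State how bottles that are never returned are handled; counting Visit 9 returns does not settle that case. State in SAP 6 that PV_PP.502 uses the same definition.

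The cost is a few lines of SAP text and a small programming change. No new data are needed, because protocol 5.1.9.1 already has the return date and capsule count recorded for each bottle.
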